In addition to therapeutic utility of acupressure, it may be cost effective by decreasing hospital stays and the need for more expensive and invasive pharmacologic interventions (9). **In this pilot feasibility study, acupressure will be used as an additional intervention to current, standard therapies.** The Near-Term Infant conceptual framework (NTI) guided the creation of our acupressure protocol to ensure incorporation of standard of care as well as optimization of acupressure elements to produce healthy outcomes in infants at risk for developing iatrogenic withdrawal syndrome. This acupressure protocol has been implemented at MCJCHV in the neonatal abstinence syndrome (NAS) population and was deemed feasible, accepted by healthcare providers and mothers, as well as safe. If proven feasible and beneficial within a PCICU population, further studies may be conducted to evaluate the efficacy of acupressure in easing with withdrawal symptoms as measured by the enhanced withdrawal assessment tool (WAT-1), when applied in conjunction with standard treatments.

Aim 1: Assess feasibility of delivering an acupressure protocol for the treatment of withdrawal in a pediatric cardiac intensive care unit. Feasibility will be assessed with successful completion of the following objectives:

- a. Achieve recruitment and consent of 4 parents per month whose infant has been exposed to opioids and/or benzodiazepines for greater than 5 days, with a retention of 80% or higher during a 24 month time period (n=40).
- b. Deliver the acupressure protocol to 20 infants at risk for developing withdrawal within the standard of care as an additional non-pharmacologic intervention (20 infants will receive standard of care).

Aim 2: Assess impact of auricular acupressure on withdrawal symptoms for an infant physically dependent on opioid and/or benzodiazepine medications. Efficacy of auricular acupressure will be assessed, in line with the standard of care, with comparison of the following assessments among intervention and control groups:

- a. Duration of opioid and/or benzodiazepine exposure
- b. Duration of wean phase
- c. Duration of mechanical ventilation
- d. Total medication dosage as measured in morphine equivalents and benzodiazepine dosages (mg/kg/patient)
- e. Hospital length of stay
- f. Severity of withdrawal symptoms as measured by the Enhanced Withdrawal Assessment Tool (WAT-1)

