- g. Presence and/or severity of delirium as measured by the Pediatric Confusion Assessment Method for the Intensive Care Unit (psCAM-ICU)
- h. Severity of agitation as measured by the Richmond Agitation Sedation Scale (RASS)
- i. Infant Pain scores as measured by Faces, Leg, Activity, Cry, Consolability Scale (FLACC)

Aim 3: Assess acceptability and implementation of the acupressure protocol as an adjunct treatment for withdrawal syndrome within the standard of care.

- a. Examine parental satisfaction of acupressure as an additional treatment as measured by the Client Satisfaction Questionnaire (CSQ8).
- b. Assess provider and staff satisfaction of acupressure as an additional therapy as measured by Acceptability of Intervention Measure (AIM), Intervention Appropriateness Measure (IAM), and Feasibility of Intervention Measure (FIM).
- c. Assess qualitative feedback as reported by parents and healthcare providers.

Impact: Results from this proposed study may expand first line, non-pharmacological therapy for infants experiencing withdrawal symptoms. Offering enhanced care for IWS infants while reducing costs related to hospital treatments is a public health concern during an opioid epidemic. Acupressure is safe, noninvasive, inexpensive, and efficiently implemented for

disorders with similar conditions to withdrawal syndrome, thus warranting additional investigation for consideration as an included standard of practice for post procedural infants.

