4.0 Inclusion/Exclusion Criteria

This prospective pilot study will be conducted over a 24-month period and will enroll a total of 40 infants. Infants will be randomized in a 1:1 ratio to the two groups; randomization will occur within REDCap. Inclusion criteria are as follows: infants, 34 weeks or greater gestation, exposure to opioids and/or benzodiazepine medications for 5 days or more, beginning a stable wean, and maternal age of 18 or older as these individuals are able to consent for themselves (see Table 2). Exclusion criteria will be captured in the medical record as follows: hemodynamic instability, transfer to another facility prior to completion of the weaning regimen or death. Parents identified by health care providers in the PCICU will be approached by study providers ([name], [name], [name], [name], or [name]) in the PCICU. Project procedures will be described and if participants would like to enroll in the study, the consent process will be completed by study providers. Following informed consent, acupressure will be administered within 24 hours MCJCHV. Healthcare providers caring for these infants will be identified through the medical record and subsequent surveys sent through their VUMC email. No ethnic group will be targeted or excluded from this study.

Table 2: Inclusion and Exclusion Criteria

Inclusion	Exclusion
34 weeks gestational age to 1 year of age	Transfer to another facility prior to wean completion
Maternal age 18 or older	Re-escalation of care/Worsening Illness
English speaking	Death
Hemodynamically stable	

Exposure to opioid and/or benzodiazepine for 5 days or more	
---	--

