receive the same assessments as non-participants and must meet the same weaning qualifications in line with the standard of care.

Acupressure Efficacy (Aim 2). As part of the standard of care, multiple metrics will be captured and compared among the intervention and control group. These include duration of opioid and/or benzodiazepine medications, duration of weaning phase, duration of mechanical ventilation, and hospital length of stay. To ensure appropriate opioid dosage comparisons, all opioid medications will be converted to morphine equivalents (mg/kg/patient); benzodiazepine medications and dosages will also be captured. Consistent with the current standard of care for infants treated in the PCICU the following assessments will be conducted: Withdrawal Assessment Tool (WAT-1) for Pediatric Withdrawal every 6 hours, Preschool Confusion Assessment Method for the ICU (psCAM-ICU) every 12 hours, Richmond Agitation-Sedation Scale (RASS) every 2-4 hours and Faces Legs Activity Cry Consolability Scale (FLACC) every 4 hours.

Acupressure Acceptability (Aim 3). Prior to discharge and after completion of the weaning protocol, parent(s) will receive the Client Satisfaction Questionnaire (CSQ8) to assess parental satisfaction of acupressure as an additional therapy. Staff and providers who cared for participants will also receive three brief electronic surveys via REDCap directly to their email prior to discharge. This survey will include 12 questions: Acceptability of Intervention Measure (AIM), Intervention Appropriateness Measure (IAM), and Feasibility of Intervention Measure (FIM) to evaluate acceptability of acupressure as a complementary therapy. Qualitative feedback back from healthcare providers and parents will be documented by administrators at time of acupressure application and skin assessment. Such feedback would include observations reported to the research team by healthcare providers or parents.

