10.0 Statistical Considerations: Analysis Plan

The study sample will be characterized using descriptive statistics including mean/median, standard deviations/interquartile range, proportions and percentages as outlined below. Benchmarks for success are summarized in Table 2.

Data Analysis Aim 1. The primary goal of this aim is to assess feasibility and implementation of this study including recruitment, retention, and execution of and adherence to the acupressure protocol. Feasibility measures will be reported as frequencies and proportions (% of eligible patients enrolled, % of patients prematurely terminating treatment, % of patients completing all study assessments, % of data collection procedures completed, % of missing medical record data). Feasibility will be determined through the following benchmarks: a) recruitment success: recruitment rate of 2 infants per month over the proposed 24-month time frame (80% of 40 (ex 32) enrolled); b) study retention: retention of >80% of participants through all assessment periods, c) adherence to the acupressure administration protocol: advanced practice providers will record at least 90% of all acupressure sessions in the REDCap database and medical record.

Data Analysis Aim 2. Descriptive data will be generated for the outcomes detailed in Table 2: Aim 2 by treatment group. Given the feasibility goal of this study, we will not conduct formal statistical tests of association between the two treatment groups, but we will provide descriptives by groups and measures of variability. These statistics will inform us of data trends. Descriptives will be generated based on the intent to treat principle.

Data Analysis Aim 3. Parental satisfaction with acupressure as an additional non-pharmacologic intervention will be reported as means with standard deviations and percentiles of the CSQ8 scores within each category of the following: excellent, good, fair and poor. Provider and staff acceptability of acupressure as an additional non-pharmacologic treatment will be measured with the Acceptability of Intervention Measure (AIM), Intervention Appropriateness Measure (IAM), and Feasibility of Intervention Measure (FIM). These measures will be reported as frequency distributions and proportions (% of AIM scores, % of IAM scores, and % of FIM scores).

Table 2: Assessment Measures

Outcomes	Measures	Time Point

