Aim 1 Feasibility of Acupressure Protocol	Demographics: age median & interquartile range, weight median & interquartile range, % male/female, % race (black, white, Hispanic)	Duration of study
	Recruitment Metrics: % of eligible patients enrolled, % of patients prematurely terminating treatment, % of patients completing all study assessments, % of data collection procedures completed, % of missing medical record data	Duration of study
	Enrollment Metrics: % of eligible patients enrolled, % of patients prematurely terminating treatment, % of patients completing all study assessments, % of data collection procedures completed, % of missing medical record data	Duration of study

	Acupressure Administration: % sticker displacement & reapplication, adverse events Infant Activity, Non-Pharmacologic Treatments	Every 24-72 hours Every 6 hours
Aim 2 Acupressure Efficacy	Duration of Medication Exposure (days): median, interquartile range Duration of Wean Phase (days): median, interquartile range Duration of Mechanical Ventilation (days): median, interquartile range Total Medication Equivalents (mg/kg/pt): median, interquartile range Hospital Length of Stay (days): median, interquartile range Exposure to adjunct medications: median, interquartile range WAT-1 Scores: median, interquartile range psCAM-ICU Scores: median, interquartile range RASS Scores: median, interquartile range FLACC Scores: median, interquartile range	Duration of study Duration of study Duration of study Every 24 hours Duration of study Every 24 hours Every 6 hours Every 12 hours Every 2-4 hours Every 4 hours
Aim 3 Acceptability	Parental Satisfaction: CSQ8 means, SD, % scores Staff/Provider Acceptability: % AIM scores, % IAM scores, % FIM scores Qualitative Feedback	Duration of study Completion of Study Every 24-72 hours

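### Aim 2g names presence of delirium as an outcome, but the planned median and IQR for psCAM-ICU cannot report how many infants were delirious

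*Combined protocol and SAP*

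**What the plan says.** Section 2.0, Aim 2g, lists among the outcomes to be compared between intervention and control "Presence and/or severity of delirium as measured by the Pediatric Confusion Assessment Method for the Intensive Care Unit (psCAM-ICU"). Section 6.1 has the instrument applied as part of standard care: "Preschool Confusion Assessment Method for the ICU (psCAM-ICU) every 12 hours". Each infant will therefore contribute a series of results.

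Section 10.0 says the Aim 2 descriptives will be those detailed in its Table 2 (Assessment Measures), by treatment group and by intention to treat. For this outcome the table's only entry is "psCAM-ICU Scores: median, interquartile range". There are no hypothesis tests: "we will not conduct formal statistical tests of association between the two treatment groups". The descriptives carry the whole of Aim 2: "These statistics will inform us of data trends".

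The opening of section 10.0 includes proportions and percentages among its descriptive statistics, but refers to what is outlined below it, and nothing below gives a percentage for delirium. No section defines a severity score for psCAM-ICU or says how the 12-hourly results are reduced to one value per infant.

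**The concern.** Presence of delirium is a yes/no result. Apart from a midpoint when the values split exactly evenly, the median of a yes/no variable is 0 or 1, and the quartiles show only whether the positive share has passed roughly 25% or 75%. The summary sorts the rate into a few wide bands and does not report the rate. Two arms in the same band get the same entry, however many infants separate them within it.

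Because Aim 2 is purely descriptive, the table row is the whole analysis of this outcome. If it does not show how many infants were delirious, the presence half of Aim 2g goes unreported as planned. The choice among ever positive, share of checks positive and days positive would then be made after the data are seen.

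**Working it through.** The documents give no delirium rate, target difference or power figure for this outcome, so there is no planned figure to reproduce. The check asks which counts of delirious infants the planned summary can tell apart.

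**Inputs from the documents**
- Arm sizes, Aim 1b in section 2.0: "Deliver the acupressure protocol to 20 infants at risk for developing withdrawal within the standard of care", and "20 infants will receive standard of care". So n = 20 per arm, consistent with section 4.0: "Infants will be randomized in a 1:1 ratio to the two groups".
- Planned summary: median and IQR (section 10.0, Table 2).
- Frequency: every 12 hours (section 6.1).

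**Assumptions**
- Presence is coded 0/1, following the aim's own word; the documents do not describe how psCAM-ICU is scored.
- For the pooled case only, 20 checks per infant (10 days at two per day); the documents give no duration.

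**Case A: one yes/no value per infant (ever delirious).** With k positives among 20 sorted values, the ones occupy ranks 21 − k to 20. Under the usual linear-interpolation definition, quantile p sits at rank 1 + 19p:
- Q1: 1 + 19 × 0.25 = 5.75, between ranks 5 and 6.
- Median: 1 + 19 × 0.50 = 10.5, between ranks 10 and 11.
- Q3: 1 + 19 × 0.75 = 15.25, between ranks 15 and 16.

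Q3 is 0 when rank 16 is still a zero, that is when 21 − k > 16, so k ≤ 4. The median is 0 when 21 − k > 11, so k ≤ 9. Q1 is 0 when 21 − k > 6, so k ≤ 14. Applying this to every k:

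| Infants positive (of 20) | Median (IQR) | Widest gap within the band |
|---|---|---|
| 0 to 4 | 0 (0–0) | 4/20 = 20 points |
| 5 | 0 (0–0.25) | none |
| 6 to 9 | 0 (0–1) | 3/20 = 15 points |
| 10 | 0.5 (0–1) | none |
| 11 to 14 | 1 (0–1) | 3/20 = 15 points |
| 15 | 1 (0.75–1) | none |
| 16 to 20 | 1 (1–1) | 4/20 = 20 points |

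The Weibull, Hazen and averaged inverted-CDF definitions give the same bands, differing only in the interpolated quartile at k = 5 and k = 15. Under the inverted-CDF definition Q3 is the value at rank 0.75 × 20 = 15, which is 0 when 21 − k > 15, so k ≤ 5. The bands become 0–5, 6–10, 11–15 and 16–20, and the widest hidden gap is 5/20 = 25 points.

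**Case B: all 12-hourly checks pooled within an arm.** There are 20 × 20 = 400 checks per arm. If every infant is positive at 4 of 20 checks, 80/400 = 20% are positive and the ones occupy ranks 321 to 400. Q3 sits at rank 1 + 399 × 0.75 = 300.25, which is a zero, so the entry is 0 (0–0). An arm with no positive check also gives 0 (0–0). The first arm has 20/20 infants ever delirious and the second 0/20. The same holds at 5% or 10% of checks.

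**What a count would show.** For 0/20 versus 4/20 the difference is 20 points. The Wilson 95% limits are 0 to 0.161 and 0.081 to 0.416, so the Newcombe interval is:
- lower: 0.20 − √[(0.20 − 0.081)² + (0.161 − 0)²] ≈ 0.00
- upper: 0.20 + √[(0.416 − 0.20)² + (0 − 0)²] ≈ 0.42

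That is about 0 to 42 points. For 6/20 versus 9/20 the same method gives 15 points, with an interval from −14 to 41. These are imprecise, but they state the rate and its uncertainty, which the planned entry does not.

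**The case against.** The strongest reply has four parts.

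**The row may concern severity.** The table refers to scores, and Aim 2g says presence and/or severity. Median and IQR suit an ordinal severity score, and also suit a per-infant number or share of positive checks. This stands as far as it goes. But no severity score or per-infant reduction is defined, and a severity summary would still leave presence unreported.

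**Large differences would show.** A reader might infer that the planned summary hides any difference in delirium, however large. It does not. Counts falling in different bands change the median or the IQR. At 10% versus 45% (2/20 versus 9/20) both medians are 0, but the IQRs are 0–0 and 0–1, so the planned entries differ. With one value per infant the hidden gap is limited to 20 points (25 under one quantile definition). The 0/20 versus 20/20 case needs pooling and a number of checks that the plan does not state.

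**The information is not lost.** A reader might also infer that Aim 2g cannot be answered, or that no delirium rate could be had for planning a later trial. Neither follows. The aim's wording allows severity, and the 12-hourly results are charted as standard care, so a count can be made from them. What is missing is the planned statistic. The general mention of percentages in section 10.0 does not supply it, because it defers to a table that specifies percentages for sex, race, recruitment and survey scores but none for this row.

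**It is one descriptive row in a 40-infant pilot.** True, and it limits the importance. The intervals above show that gaps of this size would be poorly estimated anyway. With no tests planned, however, the descriptive statistic is all that Aim 2 will deliver on delirium.

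**Conclusion.** The point holds in a limited form: the presence part of Aim 2g has no suitable planned statistic. With one yes/no value per infant and 20 per arm, the planned median and IQR can be identical for arms that differ by up to about 20 percentage points, or 25 under the inverted-CDF definition. If checks are pooled, and assuming 20 per infant, an arm with no delirium and an arm in which every infant is positive at up to 20% of checks would also look the same.

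This rests on reading presence as yes/no. The pooled figure also rests on an assumed number of checks and on a method the plan neither adopts nor rules out. The impact stays within one Aim 2 row: the section 10.0 feasibility benchmarks (recruitment, retention, adherence), the sample size and error rates are untouched.

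**What to change.** In the psCAM-ICU row of the section 10.0 assessment-measures table, replace the present entry with, for each arm:

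1. n/N (%) of infants with at least one positive check after randomisation.
2. The median and IQR, across infants, of each infant's proportion of 12-hourly checks that were positive. This fixes the infant as the unit of summary. It is needed beside the first item because an infant observed for longer has more chances to be positive at least once.
3. The median and IQR of scores only if a severity score is recorded, with that score defined in the plan.

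The cost is one edited table row. The results are already charted every 12 hours, so nothing is added to data collection or to the burden on infants and staff. Making the change before the data are reviewed also settles the choice of summary in advance.

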11.0 Privacy/Confidentiality Issues

There is a risk of breach in confidentiality; however, steps will be taken to decrease this risk as all data will be collected by the PI from the medical record then input into REDCap. Databases will only be accessible by members of the study team, password protected, and a confidential project identification number will be assigned. This information will include recruitment metrics (Aim 1), and parental satisfaction and acceptability data (Aim 3) including the following surveys: CSQ8, AIM, IAM, FIM and qualitative.

Recruitment of parents will take place during routine care. Confidentiality and privacy will be ensured by the PI and healthcare providers when discussing the study and potential participation.

12.0 Follow-up and Record Retention

All data will be stored in the Vanderbilt University Medical Center REDCap. Only authorized study personnel will have access to the password protected data tracking system and the project will have an identification number assigned. Paper copies of research records such as completed paper consent forms and surveys will be kept in a designated binder and locked cabinet in a restricted access office at Vanderbilt University Medical Center or uploaded into REDCap. The PI will manage data including quality assessment (completeness and accuracy) to ensure all variables are captured and entered into REDCap appropriately. At completion of the study, the PI will archive paper copies of research records in accordance with Vanderbilt University Medical Center's policy and as recommended by the institutional review board (IRB).

